Primary Objective: To demonstrate the equivalence in efficacy of LUBT010 to Lucentis® in terms of visual acuity, in patients with Neovascular Age-Related Macular Degeneration.		
Secondary Objectives: 
 • To assess the safety and tolerability of LUBT010 as compared to Lucentis®. • To assess the immunogenicity of LUBT010 as compared to Lucentis® 		
Study Design: Global, Phase III, Double Blind, Randomized Controlled, two-arm, interventional study in patients with neovascular AMD.		
Methodology: Eligible patients with Neovascular AMD will be randomly assigned to receive either LUBT010 0.5 mg (0.05 mL of 10 mg/mL ranibizumab) once monthly (intravitreal injection) or Lucentis® 0.5 mg (0.05 mL of 10 mg/mL ranibizumab) once monthly (intravitreal injection) for 12 months. Patients will be randomized on Day 1. Only one eye per patient will receive the investigational product (IP). Patients will visit site for a safety visit after the first dose on any day from Day 2 to Day 9, followed by the next visit on Day 31 ± 2 days, and thereafter monthly for a total of 12 months (i.e. Day 61, Day 91, Day 121, Day 151, Day 181, Day 211, Day 241, Day 271, Day 301, Day 331, and Day 360), with an allowable visit window period of ± 2 days. A post injection visit/ telephonic safety assessment after every injection will be done as deemed necessary by Investigator. Efficacy, safety, and immunogenicity assessments will be done periodically. Day 360 ± 2 will be End of Study (EOS) visit.		
Number of Patients: Adequate number of patients will be screened to randomize approximately 600 patients to 2 treatment arms in 1:1 ratio to have approximately 558 evaluable patients.		
Diagnosis and Main Criteria for Inclusion: Ambulatory male and female patients aged ≥50 years with active choroidal neovascularization (CNV) lesions involving the foveal center secondary to neovascular AMD, who are anti-VEGF naïve and having best corrected visual acuity (BCVA) in the study eye between 20/40 and 20/200 (Snellen equivalent), using Early Treatment Diabetic Retinopathy Study (ETDRS) chart testing.		
Investigational Product: The IPs will be supplied as: Test Product: LUBT010 supplied as single-use, 2-cc glass vial containing 2.3 mg of ranibizumab in 0.23 mL solution designed to deliver 0.05 mL of 10 mg/mL ranibizumab, by intravitreal injection.		

Name of Sponsor/Company: Lupin	Protocol No.: LRP/LUBT010/2016/008	
Name of Active Ingredient: Ranibizumab		
Reference Medicinal Product: EU-approved Lucentis® supplied as single-use, 2-cc glass vial containing 2.3 mg of ranibizumab in 0.23 mL solution designed to deliver 0.05 mL of 10 mg/mL ranibizumab, by intravitreal injection.		
Dose and Administration: Ranibizumab 0.5 mg (Lucentis® or LUBT010) will be administered once every month as intravitreal injection for 12 months. Total 12 injections would be given to each patient.		
Study Duration: Approximately 13 months 
• Screening Period: Maximum 28 days• Treatment and Subsequent Assessments: 12 months		
Study Endpoints: Primary Endpoint: Mean change in BCVA from baseline in the study eye at the end of 12 months, assessed with the ETDRS chart. Secondary Endpoints: Efficacy: 
• Mean change in BCVA from baseline in the study eye at the end of 3 months assessed with the ETDRS chart.• Mean change in BCVA from baseline in the study eye at the end of 6 and 9 months, assessed with the ETDRS chart. Safety: 
• Adverse Events (AE) assessment, ocular and non-ocular• Ophthalmic examination• Physical and systemic examination• Vital signs• Electrocardiogram (ECG)• Laboratory parameters: Blood (hematology and biochemistry) and urinalysis Immunogenicity: Proportion of patients with anti-drug antibodies at the end of 1, 3, 6, 9, and 12 months. Exploratory Endpoint: 
• Mean change from baseline in National Eye Institute Visual Functioning Questionnaire – 25 (NEI-VFQ-25) Version 2000 (interviewer administered) scores at 3, 6, and 12 months. Statistical Methods: The primary endpoint of change in BCVA from baseline in the study eye at the end of 12 months will be analyzed using ANCOVA model with treatment as fixed_effect, and baseline BCVA as covariate. The equivalence of efficacy will be assessed based on 90%# (two-sided) confidence interval for the difference in mean change in BCVA from baseline in the study eye at end of 12 months, with an equivalence margin of 4 letters. (# As generally required by US Food and Drug Administration [FDA]) Similarly, the equivalence of efficacy will be assessed based on 95%## confidence interval of the difference in mean change in BCVA from baseline in the study eye at the end of 12 months, with an equivalence margin of 4 letters. (## As generally required by the European Medicines Agency [EMA].) For continuous data, summary statistics will include the number, arithmetic mean, standard deviation (SD), median, minimum, and maximum. For categorical data, frequency and percentage will be presented. The safety data and immunogenicity data will be summarized and listed.		

Table 1: Schedule of Assessment

Mon=Months d=day Rand=Randomization	Screening Period		Treatment & Assessment Period (12 months)													EOS/ Early Discontinuation
	Screening Visit	Rand	Safety Visit	1 mon @	2 mon @	3 mon @	4 mon @	5 mon @	6 mon @	7 mon @	8 mon @	9 mon @	10 mon @	11 mon @ (EOT)	12 mon ²¹ (EOS)	
	(Max days)	28	Day 1 [#]	On any day from Day 2 to 9	Day 31 ± 2 d	Day 61 ± 2 d	Day 91 ± 2 d	Day 121 ± 2 d	Day 151 ± 2 d	Day 181 ± 2 d	Day 211 ± 2 d	Day 241 ± 2 d	Day 271 ± 2 d	Day 301 ± 2 d	Day 331 ± 2 d	Day 360 ± 2 d
Informed consent	X															
Demography	X															
Eligibility criteria assessment	X	X¹														
Medical & Surgical history (including Ophthalmic history)	X															
Physical & Systemic examination	X	X		X	X	X	X	X	X	X	X	X	X	X	X	X
Vital signs ²	X	X	X	X	X	X	X	X	X	X	X	X	X	X	X	X
Weight	X															
Blood sampling for laboratory investigations ³	X⁴					X			X			X				X
Urine sample for routine analysis ³	X					X			X			X				X
Urine Pregnancy Test ^{5,6}		X		X	X	X	X	X	X	X	X	X	X	X	X	X
Serum Pregnancy test ^{5,6}	X															

CONFIDENTIAL

ECG ⁷	X								X						X
IP administration (study eye only) ⁸		X ⁸		X ⁸	X ⁸										
Adverse event assessment ⁹	X	X	X	X	X	X	X	X	X	X	X	X	X	X	
Concomitant medication/treatment ¹⁰	X	X	X	X	X	X	X	X	X	X	X	X	X	X	
Refraction assessment ¹¹	X ¹²	X ¹³		X ¹³	X										
BCVA with ETDRS starting @ 4 meters ¹¹	X ¹²	X ¹³		X ¹³	X										
Ophthalmoscopic examination (Indirect dilated)	X	X ¹⁴	X	X ¹⁴	X										
Slit lamp examination	X	X ¹³	X	X ¹³	X										
Intraocular pressure measurement ¹⁵	X	X ¹⁶	X	X ¹⁶	X										
Fluorescein angiography ^{17,18}	X														
Optical coherence tomography (OCT) ¹⁷	X ¹⁹														
Blood sampling for Immunogenicity ^{13, 20}		X		X		X			X			X			X
NEI-VFQ-25		X				X			X						X

Explanation of symbols used:

[figure not shown]
- @ A post injection visit/ telephonic safety assessment after every injection will be done as deemed necessary by Investigator.
- # In the situation where the day of first dosing is different from day of randomization, all the visit days should be calculated from Day 1 (day of first dosing) rather than day of randomization.
- 1 Confirmation of eligibility (based on screening results and Investigations done on Day 1)
- 2 Includes body temperature, pulse rate, blood pressure, and respiratory rate. Should be done pre & post treatment on injection days.
- 3 **Hematology:** Complete blood count (CBC) [haemoglobin, hematocrit, red blood cells (RBCs), white blood cells (WBCs), platelets, and differential blood cell counts (neutrophils, lymphocytes, monocytes, eosinophils, basophils)]

CONFIDENTIAL

Blood chemistry: Bilirubin (total, direct, indirect), alkaline phosphatase, ALT, AST, BUN, total protein, albumin, globulin, uric acid, urea, creatinine, random glucose
Urinalysis: Appearance, color, specific gravity, pH, protein, glucose, ketones, urobilinogen, occult blood (and microscopic examination). (Repeat test can be conducted, if required. Additional investigations may be performed at the discretion of investigator to ensure subject safety.)

- 4 Including Serology: HIV, HBV (HbsAg), HCV, and Syphilis (RPR). Follicle stimulating hormone (FSH) to be done in all females at screening.
- 5 To be done in females of childbearing potential (females who are not surgically sterile or menopausal).
- 6 Serum/ Urine pregnancy test can be repeated anytime in local/ central laboratory when pregnancy is suspected in any female patient. Urine pregnancy test to be performed by the female patients themselves and the results reported to site during the visit.
- 7 Electrocardiogram (ECG) assessment can be done during any of the visits if the patient complains of any symptoms pointing towards a cardiovascular condition.
- 8 Drug to be administered as per recommendations (e.g. prophylactic antimicrobial therapy, aseptic precautions, monitoring for AEs). Patient will be observed for at least 60 min (\pm 30 min) post injection. Interval between 2 intravitreal injections of ranibizumab should not be less than 28 days
- 9 Elicit reports of any decrease in vision, eye pain, unusual redness or any other new ocular symptoms in the study eye, or any other AEs. On drug administration visits, AE assessment will be performed pre and postdose.
- 10 Includes medication for previous treatment for AMD or any other ocular condition within 3 months prior to screening and Protocol specified procedural medications (e.g. dilating drops, fluorescein dyes etc.) and pre & post medications used by the patients or any other systemic treatments
- 11 To be performed prior to dilating eyes by technicians trained and qualified to measure BCVA. BCVA assessment should begin at a starting distance of 4 meters.
- 12 Refraction and Visual acuity testing should be done prior to other ophthalmic investigations during screening. Only when the patient is eligible based on BCVA, the remaining investigations should be done. The order in which various other procedures are performed may vary from clinic to clinic, provided the procedures are completed within screening period.
- 13 To be performed pre-treatment
- 14 Predose (both eyes) & Post dose (study eye only)
- 15 Measurement method used for a patient to be preferably consistent throughout the study
- 16 Obtained pre-treatment for both eyes and 60 min (\pm 30 min) post injection for study eye only
- 17 Fundus photographs/ soft copy to be retained as source document
- 18 Known history of sensitivity to fluorescein dye to be checked before Fluorescein angiography
- 19 To be done in both eyes at screening and in study eye after every injection within a month unless not considered necessary by PI as decided by clinical examination.
- 20 Blood samples for immunogenicity to be collected, before dosing study drug (predose) at Day 1, Day 31, Day 91, Day 181, Day 271, and at EOS visit (Day 360).
- 21 In case of early discontinuations/ premature termination of the study all EOS investigations should be done on the day of termination as far as possible.

Figure 1: Study Flow Chart

- o D = Day
- o  - Lucentis® or LUBT010 injection to be given intravitreally for 12 months at following monthly visits: D1, D31, D61, D91, D121, D151, D181, D211, D241, D271, D301, and D331 with an allowable visit window period of \pm 2 days.
- o Patients will visit site for a safety visit after the first dose on any day during Day 2 to 9. A post injection visit/ telephonic safety assessment after every injection will be done as deemed necessary by Investigator. Day 331 will be the End of Treatment (EOT) visit and Day 360 will be the End of Study (EOS)visit.
- o Efficacy & Safety assessments will be done at monthly visits. Immunogenicity testing will be done at Day 1 and at the end of 1 month (D31), 3 months (D91), 6 months (D181), 9 months (D271), and 12 months (D360).

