6.3.1.1 Screening Visit (Maximum 28 days)

Screening procedures are as follows:

- Obtain written informed consent as per regulatory requirement
- Record demographic data (age, gender, race/ethnicity)
- Record medical and surgical history (including ophthalmic history)
- Record concomitant medications/treatment.
- Vital signs assessment (temperature, Pulse, blood pressure [BP], respiratory rate [RR])
- Perform physical and systemic examination
- Record weight
- Perform ECG
- AE assessment
- Perform clinical laboratory assessment (hematology, biochemistry, and urinalysis) (and any other investigation, if deemed necessary by investigator)
- Assessment of serological tests[#] for: human immunodeficiency virus (HIV), Hepatitis B virus (HBsAg), Hepatitis C virus (HCV), and syphilis (Rapid Plasma Reagins [RPR] test).
- Follicle stimulating hormone (FSH) to be done in all females at screening.

Perform serum pregnancy test in females of childbearing potential (females who are not surgically sterile or menopausal).

- Ophthalmic Examinations[@]: Unless otherwise stated these will be done for both the eyes

- Refraction assessment
- BCVA by ETDRS chart*
- Ophthalmoscopy examination (indirect dilated)
- Slit lamp examination
- Intraocular pressure (IOP) measurement
- Fluorescein angiography (FA)[#]: History of sensitivity to fluorescein dye to be checked before FA
- OCT[#]

@ Refraction and visual acuity testing should be done before pupil dilation and prior to other ophthalmic investigations. Only when the patient is eligible based on BCVA, the remaining investigations should be done. The order in which various procedures are performed may vary from clinic to clinic, provided the procedures are completed within screening period.

The period of 28 days can be relaxed up to two months for the tests marked # considering the longevity of the results for patients who may undergo rescreening (see Section 6.4.4).

* BCVA measurements should begin in a sitting position using ETDRS chart (original Sloan letter chart or number chart) at a starting distance of 4 meters (for a subject, the same ETDRS chart used at screening should be used for all subsequent visit). A standardized ETDRS chart must be used at all participating sites to minimize the assessment discrepancy. Visual acuity measurements for each eye should be obtained by an ophthalmologist or a certified examiner.

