6.3.1.2 Treatment Period (12 months)

6.3.1.2.1 Day 1 (Randomization and Ranibizumab First Dose Administration)

Randomization should be performed within maximum of 28 days of screening.

Day 1 (Predose)

- Vital signs assessment
- Urine pregnancy test (in females of childbearing potential [females who are not surgically sterile or menopausal])
- Perform physical and systemic examination
- Confirmation of eligibility based on screening results and investigations done on Day 1

- Ophthalmic Examinations: Unless otherwise stated these will be done for both the eyes
 - Refraction assessment
 - BCVA using ETDRS*
 - Ophthalmoscopic examination
 - IOP measurement
 - Slit lamp examination
- Interviewer administered NEI-VFQ-25 (baseline)
- Immunogenicity (anti-drug antibody) assessment
- Record changes in concomitant medication/treatment – if any
- AE assessment
- Randomization
- Administer study medication in study eye only (if antimicrobial therapy taken as prescribed).

Day 1 (Postdose)

- Vital signs assessment
- IOP measurement for study eye only at 60 min (\pm 30 min) post injection
- Ophthalmoscopic examination in study eye only.
- Observe for at least 60 min (\pm 30 min) postdose (post injection)
- AE assessment

Note: * notes of screening visit to be followed.

6.3.1.2.2 Day 2 to 9

The Day 2 -9 visit can be on any day from Day 2 to Day 9.

- Vital signs assessment
- IOP measurement
- Ophthalmoscopic examination
- Slit lamp examination
- AE assessment
- Inquire if antimicrobial therapy is taken as prescribed
- Record changes in concomitant medication/treatment

6.3.1.2.3 Visit Days (\pm 2 days): Day 31, 61, 91, 121, 151, 181, 211, 241, 271, and 301

Pre dose

- Vital signs assessment
- Urine pregnancy test in females of childbearing potential
- Perform physical and systemic examination
- Record ECG (only at Day 181)
- Perform clinical laboratory assessment (hematology, biochemistry and urinalysis) at Day 91, Day 181, and Day 271.
- Ophthalmic Examinations: Unless otherwise stated these will be done for both the eyes

- Refraction assessment
- BCVA using ETDRS*
- Ophthalmoscopic examination
- Slit lamp examination
- IOP measurement (Obtained pretreatment for both eyes)
- Interviewer administered NEI-VFQ-25 at Day 91 and Day 181.
- Immunogenicity (anti-drug antibody) assessment at Day 31, Day 91, Day 181, and Day 271.
- Record changes in concomitant medication/treatment
- AE assessment

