11.7 Efficacy Analysis

11.7.1 Primary Efficacy Endpoint

The primary endpoint is mean change in BCVA from baseline in the study eye at the end of 12 months, assessed with the ETDRS chart.

The primary endpoint will be analyzed using ANCOVA model with fixed-effect treatment, and baseline BCVA as covariate.

Denote the population parameter for the mean change from baseline in BCVA by θ_R for LUBT010 arm, and by θ_L for Lucentis® arm, expressed in letters. The hypothesis to be tested will be

$$H_0: \theta_R - \theta_L \leq -4 \text{ or } 4 \leq \theta_R - \theta_L \text{ versus } H_A: -4 < \theta_R - \theta_L < 4.$$

The hypothesis will be tested using the two-sided 90% confidence interval for the difference as accepted by US FDA. If the 90% confidence interval lies wholly between -4 and 4, then the

null hypothesis will be rejected. The confidence interval will be constructed using a two-sample t-test.

Similar methodology will be used with 95% CI of mean difference for EMA. Thus, if 95% (2-sided) confidence interval, lies wholly within the equivalence margin (-4, 4), then the null hypothesis will be rejected.

Missing data in the primary endpoint will be imputed by multiple imputation approach under the assumption of outcome is Missing At Random (MAR). The MAR assumption will be implemented using ANCOVA model by repeated imputation of missing values in primary endpoint. For this assumption, missing outcomes are modeled using observations from a patient's own treatment arm. Thus, MAR would tend to reflect in the missing data any observed differences between treatment groups and is appropriately conservative for the objective of assessing equivalence. Then, to assess the robustness of MAR assumption in primary analysis, the sensitivity analysis via tipping point approach under the Missing Not At Random (MNAR) assumption will be performed.

Details will be provided in the SAP, which will be finalized and signed prior to database lock and unblinding

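### Primary ANCOVA: baseline BCVA is undefined although it is measured twice before dosing, and the t-test interval sentence would drop the adjustment; a second pre-dose covariate is a small, optional gain

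*Combined protocol and SAP*

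**What the plan says.** - **Two pre-dose readings.** The Table 1 row "BCVA with ETDRS starting @ 4 meters" is marked at screening and at the randomization visit, where the footnote places it before treatment. Section 6.3.1.1 lists "BCVA by ETDRS chart" and Section 6.3.1.2.1 lists "BCVA using ETDRS" among the Day 1 pre-dose procedures, both for both eyes.
- **Gap.** "Randomization should be performed within maximum of 28 days of screening" (6.3.1.2.1).
- **Completeness.** Table 1, footnote 12: "Refraction and Visual acuity testing should be done prior to other ophthalmic investigations during screening", and only patients eligible on BCVA go on to the other screening tests. Day 1 then calls for "Confirmation of eligibility based on screening results and investigations done on Day 1". Rescreened patients repeat BCVA, because Section 6.3.1.1 relaxes the time limit only for serology, angiography and OCT.
- **Primary model.** Section 11.7.1: "The primary endpoint will be analyzed using ANCOVA model with fixed-effect treatment, and baseline BCVA as covariate". The synopsis (Statistical Methods) agrees: the endpoint will be "analyzed using ANCOVA model with treatment as fixed_effect, and baseline BCVA as covariate". There is one baseline term, and neither place says which reading it is.
- **Interval.** Section 11.7.1 also says, a few lines after the ANCOVA sentence, that the confidence interval is built from a two-sample t-test.
- **Definition of baseline.** The only explicit link between baseline and Day 1 is for the NEI-VFQ-25 (6.3.1.2.1 and 8.2).
- **Sample size.** Section 11.1 uses SD 14.5 letters, margin 4 letters, a two-sided 5% level, 80% power, 279 per arm and 7% dropout, with no credit for covariate adjustment.

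**The concern.** Baseline BCVA enters the primary analysis twice: it is subtracted to form the change score, and it is the covariate. Choosing the screening value, the Day 1 value or a mean gives the same patient a different endpoint value. That choice should be fixed before anyone can see its effect.

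The two statements about the interval are also incompatible as written. A two-sample t-test on change scores uses no covariate. If the deciding interval came from it, the ANCOVA would play no part in the equivalence conclusion.

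Finally, one ETDRS score carries test-retest error, so adjusting for a single reading leaves some removable variance in the residual. The screening score is a second reading of the same variable. It precedes randomization and should be nearly complete. Equivalence turns on whether an interval fits inside ±4 letters, so avoidable width lowers the chance of a correct conclusion.

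**Working it through.** **1. The plan's own figure.** From Section 11.1: SD 14.5, margin 4, 0.025 per side, power 80%. A true difference of 0 is assumed, as the plan does not state one.

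n per arm = 2 × [14.5 × (1.960 + 1.282) / 4]² = 276.1, so 277 (278 with the exact t). The plan has 279. With SE = 14.5 × √(2/279) = 1.228 letters, power = 2Φ(4/1.228 − 1.96) − 1 = 80.6% (80.4% with t). 558/0.93 = 600. The stated design reproduces.

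**2. Model for the second covariate.** The documents give no baseline SD, test-retest error, slope or drift. Assumed ranges:

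| Input | Range | Mid case |
|---|---|---|
| Observed baseline SD (S) | 10–14 letters | 12 |
| Error SD of one score (e) | 3–7 letters | 5 |
| Slope of Month 12 on true baseline (b) | 0.7–1.0 | 0.85 |
| Drift SD, screening to Day 1 (d) | 0–3 letters | 3 |

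Day 1 score X1 = T + e1; screening score X0 = T + drift + e0; Month 12 score Y = bT + noise. The SD of Y − X1 is held at 14.5.

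**3. Mid case.**
- Var(T) = 144 − 25 = 119; Cov(Y, X1) = Cov(Y, X0) = 0.85 × 119 = 101.15.
- Var(Y) = 210.25 − 144 + 2 × 101.15 = 268.55.
- Day 1 alone: 268.55 − 101.15²/144 = 197.50, residual SD 14.05.
- Var(X0) = 119 + 9 + 25 = 153; Cov(X1, X0) = 119; implied correlation 119/√(144 × 153) = 0.80.
- Both: 268.55 − 101.15² × (144 + 153 − 2 × 119)/(144 × 153 − 119²) = 191.86, residual SD 13.85.
- SE falls 1.4% and variance 2.9%, so 558 × 0.029 ≈ 16 patients. Power (95% interval, 279 per arm) goes from 83.9% to 85.3%.

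**4. Sensitivity.**
- If 5 letters is the SD of a difference between two tests, one score has error 5/√2 = 3.5. Residual SD then goes from 14.25 to 14.15: 0.7% of SE, about 8 patients, power 82.5% to 83.2%.
- Over the whole grid, SE falls 0.3% to 4.1%. The top needs S = 14, e = 7, b = 1.0 and d = 0 together. With S = 10 the ceiling is 2.3%.
- A second parameterization (baseline SD 13, slope 0.8, two exchangeable readings with correlation r) starts at residual SD 14.26 and power 82.2%. It reaches 82.9%, 83.7% and 85.2% at r = 0.95, 0.9 and 0.8, worth about 8, 16 and 33 patients.

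**5. Averaging instead.** In that second parameterization, if screening adds nothing once Day 1 is known, the simple mean raises residual variance by 2.7% at r = 0.9 (power 82.2% to 80.7%) and by 5.3% at r = 0.8 (to 79.3%). A second covariate then gains about nothing, and costs one of about 555 residual degrees of freedom, under 0.2%.

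**6. t-test against ANCOVA.** In the same central case, an unadjusted interval gives 80.4% power against 82.2% for the Day 1 ANCOVA, a difference of 1.8 points. In the mid case of step 3 it is 80.6% against 83.9%.

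**The case against.** A reader might infer that the plan throws away precision it has already paid for. The documents do not show this. If baseline is undefined, a mean of the two readings is not ruled out, and Section 11.7.1 defers details to a SAP that is not in the text reviewed.

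The context does lean towards Day 1: BCVA is taken pre-treatment at that visit, and the questionnaire given there is labelled as baseline. The t-test sentence may be loose wording for a t-based interval from the ANCOVA. Both readings are reasonable guesses, but the text confirms neither. The primary variable and the deciding interval should not depend on guesses.

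A single-baseline ANCOVA is valid, and the sample size does not rely on adjustment. A reader might therefore infer that the trial is underpowered without the second reading; step 1 shows that it is not.

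The size of the gain is also open to challenge, and most of that challenge stands:
- All four inputs are assumed, and the mid case implies a correlation of 0.80, the low end of the 0.8 to 0.95 range considered.
- The 20/40 to 20/200 window spans about 35 letters (assuming 5 letters per 0.1 logMAR). A uniform spread over it has SD 35/√12 ≈ 10, so 12 to 14 may be high.
- Up to 28 days of untreated active disease, and selection on acuity, weaken the link between the two readings.

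These points lower the expected gain and argue against averaging. They do not make a second covariate harmful.

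**Conclusion.** The point holds in a limited form. BCVA is measured twice before dosing, the primary model names one baseline without identifying it, and Section 11.7.1 describes the deciding interval in two incompatible ways. The stated 558 evaluable patients, 600 randomized and 80% power are correct on the plan's own inputs.

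The second covariate is a minor improvement. Its gain is roughly 0.3% to 4% of the SE and more plausibly 0.7% to 1.5%, which is about 8 to 16 of 558 patients or 0.7 to 1.4 power points at zero true difference. It could be near zero. These figures rest wholly on assumed baseline SD, test-retest error, slope and drift. Under the central assumptions, reconciling the interval sentence matters at least as much.

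**What to change.** Before unblinding, in Section 11.7.1 and the synopsis:

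1. Define baseline as the Day 1 pre-dose study-eye BCVA, for both the change score and the covariate.
2. Take the deciding 90% and 95% intervals from the ANCOVA treatment difference, and remove the two-sample t-test sentence.
3. Add screening study-eye BCVA as a second continuous covariate, not averaged with Day 1, in the primary ANCOVA and in the imputation model.

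The cost is a few lines of wording and one degree of freedom for item 3. No new data are needed, the treatment comparison is not biased because both readings precede randomization, and the endpoint and sample size stay as they are. Items 1 and 2 are needed whether or not item 3 is adopted.
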